We propose a single arm trial of TB preventive therapy to assess its toxicity, measure adherence, and determine whether its benefits outweigh its risks when given to TB/HIV-infected drinkers (n=200). We will provide 6 months of INH to HIV/TB infected drinkers (n=200) and non-drinkers (n=100) to describe safety, tolerability, and adherence among drinkers and by level of drinking. We will conduct frequent monitoring for toxicity, and assess toxicity as well as adherence. We will evaluate the safety, tolerability and adherence by level of drinking, measured by self-report and augmented by phosphatidylethanol (PEth), an established biomarker for alcohol consumption. We will employ objective measures of adherence, including electronic medication monitoring (EMM) of pill bottle opening, pharmacy pill counts, and a novel measure of INH exposure, that is, INH concentration in hair. We will actively monitor for toxicity, using the U.S. standard of care for laboratory monitoring during TB preventive therapy for heavy drinkers. We will use the safety, tolerability, and adherence results, together with the known efficacy and mortality benefit of TB preventive therapy in HIV-infected persons in SSA, and our established decision analytic model of TB preventive therapy, to determine whether the mortality and quality of life benefits of TB preventive therapy outweigh the toxicity risks for HIV-infected drinkers in resource limited settings.

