Primary analysis: Safety. The focus of this aim is the evaluation of safety among drinkers overall (primary) and by drinking levels (secondary). Thus the primary analysis set will be all participants who receive at least one dose of TB preventive therapy who are current drinkers. We will report the incidence of Grade 3/4 hepatotoxicity at any time during prescribed treatment along with 95% exact binomial confidence intervals (CIs).

Secondary analyses: Safety and tolerability will be estimated by level of alcohol use at baseline and during treatment. To examine safety and tolerability by alcohol consumption prior to treatment, we will report hepatotoxicity and treatment discontinuation stratified by level of drinking (heavy alcohol consumption, current but not heavy drinking, no drinking) at baseline. Fisher's exact test and exact logistic regression models adjusting for gender, hepatitis B co-infection, Cd4 cell count and/or viral suppression will be used to compare safety outcomes across drinking levels. To inform clinical practice, we will also report the outcomes by self-reported alcohol consumption levels using the AUDIT-C and the CAGE. We will also examine toxicity by level of PEth, using recently suggested PEth cutoffs. We will use generalized estimating equation logistic regression models to examine whether drinking level during the treatment period impacts safety and tolerability outcomes.

Secondary analysis: Comparison of hepatotoxicity rates to previous studies. We will also compare estimates and 95% CIs to those reported in published studies of TB preventive therapy in those with HIV, which found hepatotoxicity rates of 0.3-5.5%.

Sample size justification. We anticipate a total of 200 drinkers will be enrolled into the current study. Based on the Uganda ARCH cohort retention, we expect 90% 6-month study visit retention resulting in N=180 evaluable participants. We expect that the proportion of participants with any Grade 3/4 hepatotoxicity within the treatment period will be approximately at the midpoint of the range of toxicity rates published previously, i.e. 2.6%. Given this, we would expect approximately 5 safety events, and the length of a 95% exact binomial CI around the estimate would be 5.5%, (i.e. 0.9% to 6.4%).

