To illustrate power for secondary analyses, we also calculate the minimum detectable difference to compare safety between alcohol groups. I.e., to compare toxicity between any group of drinkers (either heavy drinkers or moderate drinkers, each expected to be approximately 1/3 of the sample) to non-drinkers (1/3 of the sample), we will have 80% power to detect a difference in toxicity rate of 0.095 or greater if the toxicity rate in the lighter drinkers/abstainers is 1% and alpha is set to 0.05 based on a Fisher's Exact test.

C.3.10 Statistical analyses for Aim 2.

Primary analysis: The goal of this aim is to estimate the level of adherence overall among drinkers and by drinking level (including abstainers). The analysis will consist of all participants enrolled. For those who are advised to discontinue therapy by the study physicians, adherence up until discontinuation will be used; however, additional sensitivity analyses will be conducted using alternative imputation strategies (e.g. using the midpoint between best and worst weeks, and assuming the worst case scenario of zero for the discontinued time period). We will report the percent adherence using EMM data over the treatment duration and 95% CIs overall among drinkers and by drinking level (heavy, non-heavy, abstainer), and fit multiple linear regression models, controlling for gender, to compare adherence across drinking categories. If the data are skewed, transformations will be performed (e.g., log transformation) or median regression if no appropriate transformation is identified.

Secondary analyses: Alternate measures of adherence and adherence over time and by level of alcohol use. Secondary measures of adherence will be analyzed using the same approach as described above. We will additionally conduct all adherence analyses excluding the first 40 days to remove a possible Hawthorne effect that may occur when patients are aware they are being monitored, but that often abates after one month. We will also conduct repeated measures analyses of monthly adherence data using linear mixed effects regression models, with month on treatment included as a predictor, to test the hypothesis that adherence changes over time. We will additionally use these analyses to assess whether drinking level at baseline and during treatment (using time-updated covariates) impact adherence.

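### The on-treatment drinking analysis fits a large-sample GEE logistic model to about five hepatotoxicity events, with no stated coding of drinking and no sparse-data fallback

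*Combined protocol and SAP*

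**What the plan says.** Section C.3.9 (secondary analyses) treats the two drinking questions differently. Baseline drinking, in three levels, is compared with Fisher's exact test and exact logistic regression. For drinking on therapy the whole specification is: "We will use generalized estimating equation logistic regression models to examine whether drinking level during the treatment period impacts safety and tolerability outcomes". No coding, working correlation, covariates or sparse-event rule is attached to that sentence.

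The sample size text in C.3.9 shows how few events there will be. The rate in drinkers is put "approximately at the midpoint of the range of toxicity rates published previously, i.e. 2.6"%, so that "we would expect approximately 5 safety events". The power illustration takes three groups ("either heavy drinkers or moderate drinkers, each expected to be approximately 1/3 of the sample) to non-drinkers (1/3 of the sample") and holds "if the toxicity rate in the lighter drinkers/abstainers is 1% and alpha is set to 0.05 based on a Fisher's Exact test".

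Three other places bear on the point:
- C.3.6 stops treatment when a Grade 3/4 toxicity develops. It schedules PEth blood draws at baseline and months 3 and 6, with brief alcohol surveys at the monthly visits.
- C.3.8 defines the safety outcome as any such event during the treatment period.
- C.3.11 plans an exploratory lasso with time-updated heavy drinking among the predictors, chosen because events are few.

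**The concern.** GEE inference relies on large-sample theory with robust standard errors. What counts here is the number of events, not the number of visits. Because treatment stops at a Grade 3/4 event, each person contributes about one event at most, and seven on-treatment visits per person add rows but almost no information. If a drinking level has no events, its log odds ratio has no finite estimate and its robust standard error means nothing. Even when every level has an event, each estimate rests on a handful of people.

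The plan recognises sparse data for baseline drinking and for the exploratory predictors, but not for this analysis. The study is meant to inform guidance on drinkers. An unstable answer about drinking during isoniazid could be read as reassurance or as alarm, with little behind either.

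**Working it through.** **Inputs.**
- Enrolment (Study Design Overview): "We will provide 6 months of INH to HIV/TB infected drinkers (n=200) and non-drinkers (n=100").
- Three levels of one third each, so 100 per level (C.3.9).
- Retention (C.3.9): "we expect 90% 6-month study visit retention resulting in N=180 evaluable participants". Applying 90% to non-drinkers as well is my assumption and gives 90 per level.
- Rates: 2.6% in drinkers. The 1% for lighter drinkers/abstainers is a conditional power input. Using 1% for non-drinkers and 2.6% for both drinker levels is my assumption.

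**1. The plan's own figures.** The exact binomial interval for 5/180 is 0.91% to 6.36%, which agrees with the stated 0.9% to 6.4%. Two-sided Fisher power for 1% v 10.5% (difference 0.095) is 80.7% at 100 per group, which reproduces the stated 80%. At 90 per group it is 74.2%.

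**2. Chance of an empty level, three-level coding.** P(at least one empty) = 1 − Π[1 − (1 − p)^n].
- n = 100: 0.99^100 = 0.366 and 0.974^100 = 0.072, so 1 − (1 − 0.366)(1 − 0.072)² = 0.454.
- n = 90: 0.99^90 = 0.405 and 0.974^90 = 0.093, so 1 − (1 − 0.405)(1 − 0.093)² = 0.511.
- The non-drinker level alone is empty in 37% (n = 100) or 40% (n = 90). Every contrast against it is then non-finite.

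A visit-level simulation (4,000 trials, seven visits, follow-up ending at the event, fixed levels of 100) gave 44.9%. Letting drinking level change at assumed rates of 10% or 25% per visit gave 44% to 56%; the documents give no switching rate.

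**3. Other codings and inputs.**
- Heavy v everyone else, n = 100: 1 − (1 − 0.974^100)(1 − 0.99^100 × 0.974^100) = 0.096. At n = 90 it is 0.128.
- Drinkers only, heavy v not heavy: 14% to 30%, depending on group sizes.
- Any drinking v none: 37% (100 v 200) or 41% (90 v 180).
- Three levels, with 73% of drinkers heavy as in the source cohort (Table 2): 53% enrolled, 58% retained.
- Three levels, with 1% in both lighter drinkers and abstainers: 63% or 68%.
- The midpoint of the quoted 0.3-5.5% is (0.3 + 5.5)/2 = 2.9%, not 2.6%. Using 2.9% gives 43% or 49%, so nothing turns on it.

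**4. What separated fits report.** I fitted an independence GEE with robust standard errors, seven visits and 100 people per level. The levels are listed with the reference first.
- Events 0/3/2: the software reported convergence, with coefficients of about 23, standard errors of about 535 and p about 0.97.
- Events 1/3/0: the software reported convergence, with a coefficient of about −22 and p about 10^−106 for the empty level.

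**5. Power, two fixed groups of 100, by exact enumeration.** The Wald test uses log OR/SE with SE² = the sum of reciprocal cell counts, and a non-finite result counts as no rejection. The Firth test is the penalised likelihood ratio on 1 df.

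| Rates | Wald, finite fits only | Wald, all trials | Fisher | Firth |
|---|---|---|---|---|
| 1% v 10.5% | 76% | 48% | 81% | 88% |
| 1% v 2.6% | 0.3% | 0.2% | 1.9% | 5% |

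A visit-level GEE simulation with rates of 1%, 10.5% and 10.5% agreed on heavy v non-drinkers: 74% of finite fits and 47% of all trials rejected.

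**6. Null behaviour (2.6% everywhere, 100 per level).** Firth rejects in 2.4% of trials with two groups and 2.6% with three, so its gain is not bought with excess false positives. The three-level Wald test rejects in 0.5% of finite fits, against a nominal 5%.

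**The case against.** The strongest reply is that the GEE sentence does not commit to three levels. Three levels are stated for baseline drinking, and the only time-updated drinking predictor the plan names for toxicity is heavy use (C.3.11). Coded as heavy v everyone else, an empty level arises in about 10-13% of trials, and that coding could be adopted without leaving GEE. This stands, and it rules out quoting 45% without its assumptions. It does not remove the problem: the coding is unstated, a 10% risk still needs a rule, and the Wald test remains poorly calibrated with so few events.

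A reader might also infer that the model is near-powerless whenever it fits. The documents do not support that. At the plan's own detectable difference, 76% of finite fits reject. At 1% v 2.6% the lack of power is shared by Fisher and Firth and comes from the small number of events, not from GEE.

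Nor is this the only planned look at drinking on therapy, since the C.3.11 lasso includes time-updated heavy drinking. However, that analysis is exploratory, selects variables on a grouped outcome of hepatotoxicity and/or discontinuation, and is not named as a fallback.

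The harm should not be described as only a false null, because the separated fits went both ways. Finally, the documents give no expected discontinuation rate, so none of these percentages applies to tolerability.

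**Conclusion.** The concern holds in limited form. The method named for on-treatment drinking and Grade 3/4 hepatotoxicity does not suit the number of events the plan expects. With three levels and rates of 1%, 2.6% and 2.6%, at least one contrast has no finite estimate in about 45% of trials (51% after 10% loss). With heavy v everyone else the figure is about 10-13%, and the plan does not say which coding applies. Where the plan's own detectable difference is real, the Wald test gives up about a third of all trials' power relative to Fisher (48% v 81%, 33 percentage points), mainly because the 1% group is often empty.

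These figures assume fixed groups, the illustrative 1% rate and hepatotoxicity only. The analysis is secondary and the primary exact interval is untouched. The change should be made but is not essential to the trial's main result.

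**What to change.** For Grade 3/4 hepatotoxicity, replace the GEE sentence with Firth-penalised logistic regression, using penalised-likelihood confidence intervals and tests, on person-visit records up to and including the first event. With at most one event per person, no working correlation is needed. Make time-updated heavy v not heavy the main contrast.

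State how heavy status is set at visits without a PEth result, for example from that visit's self-report together with the most recent PEth.

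For tolerability, use the same model if discontinuations prove similarly few.

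The cost is a few sentences in the SAP, using standard software and data already being collected. The downside is slight shrinkage of estimates towards no effect. The change does not create power at 1% v 2.6%, so a non-significant result should be reported with its interval and not as evidence that drinking on treatment is safe.

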Heavy drinking is common among HIV-infected persons and heavy drinkers are at high risk for active TB. In several studies of persons in HIV care in SSA, a median of 25% of persons self-reported heavy drinking,¹²⁻¹⁷ with heavy drinking defined as exceeding the NIAAA drinking limits (Table 1) or via the Alcohol Use Disorders Identification Test – Consumption (AUDIT-C).^{34,35} Heavy alcohol consumption is an established risk factor for HIV infection,^{36,37} and is also a risk factor for becoming infected with TB via increased immune system suppression and time spent in settings where TB is prevalent.²⁰ The risk of active TB is increased 3-fold among heavy drinkers compared to non-drinkers,^{18-20,38} and heavy drinkers are more likely to have smear positive disease, slower TB treatment response, and higher mortality while on TB treatment.^{20,39} Thus, HIV-infected drinkers are at high risk of morbidity and mortality due to active TB disease.

Preventive treatment for TB is life-saving among persons with HIV. Randomized trials conducted prior to widespread ART use showed high efficacy of IPT to prevent TB in those with HIV.⁴ Recent studies, including the TEMPRANO ANRS trial, showed the additive benefit of IPT and ART in reducing mortality for patients at all CD4 counts.^{4-6,8} IPT-associated decreases in active TB and mortality ranged from 30% to 50%, supporting the concomitant use of IPT and ART. Thus the WHO recommends IPT, intensified TB case-finding, and infection control for persons with HIV. Major implementation of IPT in HIV-infected persons in South Africa is underway,¹ scale up is occurring in Tanzania⁴⁰ and Botswana,⁴¹ and calls for further roll-out have been made.^{10,11}

The WHO lists “regular and heavy alcohol use” as a contraindication to IPT, but data on the hepatotoxicity of IPT in HIV-infected drinkers are limited. INH is metabolized by the liver, and the rate of Grade 3/4 (serious) hepatotoxicity due to INH ranges from 0.1-4.0% of all patients.⁴² Most INH-associated hepatotoxicity is reversible by stopping therapy, but liver injury can, rarely, lead to the need for liver transplantation or death, with mortality rates of 0.05-0.10%.⁴³ In the U.S., concern about toxicity is mitigated by the ability to perform liver enzyme monitoring in patients deemed at highest risk of INH-related hepatitis.⁴⁴

Table 1. Frequently used acronyms and definitions

6H	6 months daily INH
ALT/AST	Alanine and aspartate aminotransferases

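### Does it matter that the 2.6% planning rate is not the midpoint of the published 0.3–5.5% toxicity range, and that precision is given for 180 drinkers when the primary set is all those dosed?

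*Combined protocol and SAP*

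**What the plan says.** All the relevant text but one sentence is in section C.3.9 (Statistical analyses for Aim 1).

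- **Primary set.** Under the primary safety analysis, "the primary analysis set will be all participants who receive at least one dose of TB preventive therapy who are current drinkers". The result is reported as an incidence with a 95% exact binomial interval.
- **Published range.** The secondary comparison with earlier studies of preventive therapy in people with HIV cites work "which found hepatotoxicity rates of 0.3-5.5" per cent.
- **Planning rate.** The sample size justification puts the expected proportion with Grade 3/4 hepatotoxicity "approximately at the midpoint of the range of toxicity rates published previously, i.e. 2.6" per cent. It does not repeat the end-points of the range or cite a source for them.
- **Numbers.** "We anticipate a total of 200 drinkers will be enrolled into the current study", and "we expect 90% 6-month study visit retention resulting in N=180 evaluable participants".
- **Precision.** "Given this, we would expect approximately 5 safety events, and the length of a 95% exact binomial CI around the estimate would be 5.5" points, given as 0.9% to 6.4%.

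The remaining sentence is in section B (Background and Significance), which gives a second range, for isoniazid in general: "the rate of Grade 3/4 (serious) hepatotoxicity due to INH ranges from 0.1-4.0% of all patients".

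**The concern.** Two things look wrong on reading the paragraph.

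First, the midpoint of 0.3–5.5% is 2.9%. The figure 2.6 is half the width of that range, which suggests a half-width was taken for a midpoint, although the document does not say how the figure arose. Safety is the sole primary outcome, and this is the only planning calculation for it. A wrong input could mean that the event count and interval width offered in support of 200 drinkers are also wrong.

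Second, the interval is worked out for the 180 drinkers expected at the 6-month visit, while the primary set is every current drinker who takes a dose. Staying to month 6 is not a condition of that set, so the quoted precision seems to describe a different population from the one to be analysed.

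If either point changed the expected precision materially, the justification for the number enrolled would need to be reworked.

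**Working it through.** **Inputs** (section C.3.9 unless noted): 200 drinkers enrolled; 90% retention; planning rate 2.6%; published range 0.3–5.5%; second range 0.1–4.0% (section B); two-sided 95% exact (Clopper-Pearson) interval.

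**1. The plan's own figure.**
- Evaluable drinkers: 200 × 0.90 = 180.
- Expected events: 180 × 0.026 = 4.68, rounded to 5.
- Clopper-Pearson limits for x events in n are the 2.5% quantile of Beta(x, n − x + 1) and the 97.5% quantile of Beta(x + 1, n − x).
- For 5/180 = 2.78%, the limits are 0.91% and 6.36%, length 5.46 points.

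This reproduces the printed 0.9% to 6.4% and 5.5 points.

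**2. The midpoint.**
- 0.3–5.5%: (0.3 + 5.5)/2 = 2.9%; half-width (5.5 − 0.3)/2 = 2.6%.
- 0.1–4.0%: (0.1 + 4.0)/2 = 2.05%.
- Mixed end-points: (0.3 + 4.0)/2 = 2.15% and (0.1 + 5.5)/2 = 2.8%.

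No range printed in the document has 2.6% as its midpoint.

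**3. Effect of using 2.9% with 180 drinkers.**
- Expected events: 180 × 0.029 = 5.22, again rounded to 5.
- The interval is therefore the same 0.91% to 6.36%.
- Any planning rate from 4.5/180 = 2.50% up to just under 5.5/180 = 3.06% rounds to 5 events, so 2.6% and 2.9% cannot be told apart at this step.
- The printed interval belongs to 5/180 = 2.78%, which lies between the two rates and slightly nearer 2.9%.

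**4. Effect of using all dosed drinkers** (assuming all 200 take a dose and are fully observed).

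| Rate | Expected events | Rounded | Estimate | Exact 95% CI | Length |
|---|---|---|---|---|---|
| 2.6% | 200 × 0.026 = 5.2 | 5 | 2.50% | 0.82–5.74% | 4.92 |
| 2.9% | 200 × 0.029 = 5.8 | 6 | 3.00% | 1.11–6.42% | 5.31 |

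**5. Check without rounding the event count.** The expected length is the sum over k of Binomial(k; n, p) × length(k, n).

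| | n = 180 | n = 200 |
|---|---|---|
| p = 2.6% | 5.19 | 4.90 |
| p = 2.9% | 5.44 | 5.13 |

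All four values are below the stated 5.5 points.

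**The case for a change.** The best case for a change is that the primary analysis is pure estimation, so the planning rate and interval length are the whole statistical argument for 200 drinkers. The same section will later set the observed rate beside 0.3–5.5%, and a reader will notice that the stated midpoint is not the midpoint of that range. The word approximately does not rescue the sentence, because a specific value follows, given to the same decimal place as the end-points. The precision for the defined primary set is also absent, and a participant who leaves early still belongs to that set, since toxicity is assessed from week 2 (section C.3.6). Correcting both would take two sentences.

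The first part stands as a matter of wording: 2.6% does not follow from the only HIV-specific range shown. Two qualifications apply. The sample size sentence does not name its range, so the link to 0.3–5.5% rests on its being in the paragraph just before. That range is also quoted without a grade, whereas 2.6% refers to Grade 3/4 events. An unprinted source range cannot be excluded.

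The second part does not stand as an error. Planning on a number reduced for attrition while analysing everyone dosed is ordinary practice, and the plan says openly that it does so. Putting 200 into the exact formula treats the 20 or so drinkers expected to be lost by month 6 (200 − 180) as fully observed. Section C.3.13 foresees multiple imputation if data are missing at random, which would not restore the precision of 200 complete records. Those lost still contribute their earlier visits, so the information lies somewhere between 180 and 200, and 180 is the cautious choice.

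**Conclusion.** No change follows. The description of 2.6% as roughly the midpoint is a clerical slip, assuming that 0.3–5.5% is the range meant; the gap is 0.3 percentage points in an assumption that is itself marked as approximate. Using 2.9% leaves the 180 evaluable drinkers, the 5 expected events and the interval of 0.9% to 6.4% exactly as printed. No hypothesis test, margin or power for the primary endpoint depends on the rate, and the reported result will rest on the observed count.

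Giving precision for the all-dosed set is a presentational preference. It would shorten the quoted length from 5.5 points to between 4.9 and 5.3 if all 200 were dosed and fully observed, which informs no decision. The stated figure errs slightly on the safe side under every combination of rate and number checked. The estimator, analysis set and sample size are unaffected.
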